### B.9.2.2 Secondary Analyses

The following *secondary endpoints* will be evaluated:

- If the primary efficacy endpoint in the test group is found to be superior to that in the control group, then a secondary endpoint will evaluate whether the proportion of subjects who achieve a 50% improvement in their back pain VAS score at 1, 3, 9, 12, 18 or 24 months in the test group is superior to that in the control group. A superiority test based on the difference in proportions will be performed based on the following null hypothesis, with a two-sided p-value of 0.05 or less considered evidence of statistical significance.

$H_0$ : The proportion of subjects (P) who achieve a 50% improvement in their back pain VAS score at 1, 3, 9, 12, 18, or 24 months in the Test group is less than or equal to that in the Control group.

$$P_{\text{Test}} = P_{\text{Control}}$$

$H_1$ : The proportion of subjects (P) who achieve a 50% improvement in their back pain VAS score at 3 months in the Test group is greater than that in the Control group.

$$P_{\text{Test}} \neq P_{\text{Control}}$$

- Change in mean VAS will be evaluated with two-sample t-test of non-inferiority in means with a 0.65 cm non-inferiority margin at 6 months.

$H_0$ : The change (C) in subject's VAS pain intensity score relative to baseline at the Primary Efficacy Assessment in the Test group is worse than that of subjects in the Control group by more than 0.65 cm.

$$C_{\text{Test}} \geq C_{\text{Control}} + 0.65 \text{ cm}$$

$H_1$ : The change (C) in subject's VAS pain intensity score relative to baseline at the Primary Efficacy Assessment in the Test group is no more than 0.65 cm worse than the mean change from baseline in the control group.

$$C_{\text{Test}} < C_{\text{Control}} + 0.65 \text{ cm}$$

The non-inferiority margin of 0.65 cm was selected based on a previous study of a similar therapy against traditional SCS. In that study, the experimental therapy showed a 4.9 point improvement while traditional SCS showed a 3.6 point improvement for a difference of 1.3 points. Taking 50% of this treatment effect yields the margin of 0.65 cm. If the null hypothesis is successfully rejected for the non-inferiority test, a test for superiority of treatment to control will be performed based on a two-sided 0.05 alpha level.

The following secondary endpoints do not have an associated hypothesis, and no significance level will be assigned to statistical tests that may be performed.

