3.2 Blinding

Due to the nature of the treatment groups, comparing an implantable medical device with conventional medical management that may involve multiple different treatments, it is not feasible to blind the subjects, implanting physicians or the clinical site personnel to the group assignments. The assessment of treatments are done by the subjects and not by the site personnel, so the lack of blinding of site personnel should not affect results as pain is the major assessment and subjects tend to describe pain truthfully since it affects their everyday life dramatically and not be influenced by knowledge of which treatment arm they are assigned to. In order to minimize potential assessment bias, the subjects will receive the standard instructions for completing the questionnaires.

4 Sample Size Determination

The clinical investigational plan requires a screening process for all subjects that provide written informed consent. These subjects will undergo screening to assess eligibility. Subjects may be excluded for various reasons during screening. Accordingly, in order to include an estimated 150 subjects to the point of randomization, up to 300 subjects may need to be consented and enrolled to account for exclusions prior to randomization.

The sample size estimate to determine primary endpoint is based on the primary objective of demonstrating superiority of the test group to the control group. Established methods were followed in determining the superiority criteria and the related sample size estimate

- Test basis: Pearson Chi-square binomial test for superiority
- Estimated responder rate of 60% in the test group and 30% in the control group
- Significance level, alpha, of 0.05 two-sided
- Randomization: 1:1

With these assumptions, a sample size of 50 subjects in each group will result in greater than 85% power for the study.

Based on the primary endpoint requirement, a minimum of 50 subjects per treatment group are required (100 total). To account for a combined estimated attrition of 33% for subjects that do not complete the Trial Phase, and subjects that exit study before the 6-month primary endpoint visit, approximately 150 subjects would need to be randomized.

To account for 50% attrition prior to randomization (including subject ineligibility after signing the informed consent and subject dropout), it is estimated that a total of up to 300 subjects would need to be enrolled in the study.

Statistical Analysis Plan		Page 7 of 14

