5.7.1.1 Primary Analysis

The *primary efficacy endpoint* will be evaluated with a Pearson Chi-square binomial test for superiority at the two-sided 0.05 alpha level.

H_0 : The percentage of subjects (P) who achieve a 50% improvement in their back VAS pain score at 6 months in the Test group is the same as in the Control group.

$$P_{\text{Test}} = P_{\text{Control}}$$

H_1 : The percentage of subjects (P) who achieve a 50% improvement in their back VAS pain score at 6 months in the Test group is superior to that in the Control group.

$$P_{\text{Test}} \neq P_{\text{Control}}$$

Primary analysis will be based on the mITT analysis set.

In addition to the results from the hypothesis test, the numerator and denominator and percentage responders will be presented.

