5.7.2 Secondary Endpoints

The following secondary endpoints will be evaluated:

- If the primary efficacy endpoint in the test group is found to be superior to that in the control group, then a secondary endpoint will evaluate whether the proportion of subjects who achieve a 50% improvement in their back pain VAS score at 1, 3, 9, 12, 18 or 24 months in the test group is superior to that in the control group. A superiority test based on the difference in proportions will be performed based on the following null hypothesis, with a two-sided p-value of 0.05 or less considered evidence of statistical significance. A separate hypothesis test will be conducted for each time point.

Statistical Analysis Plan		Page 11 of 14
Sponsor	Study	Version
SGX International	EU RCT DTM SCS vs. CMM	3.0

H_0 : The proportion of subjects (P) who achieve a 50% improvement in their back pain VAS score at 1, 3, 9, 12, 18, or 24 months in the Test group is less than or equal to that in the Control group.

$$P_{\text{Test}} = P_{\text{Control}}$$

H_1 : The proportion of subjects (P) who achieve a 50% improvement in their back pain VAS score at 1, 3, 9, 12, 18, or 24 months in the Test group is greater than that in the Control group.

$$P_{\text{Test}} \neq P_{\text{Control}}$$

- Change in mean VAS will be evaluated with two-sample t-test of non-inferiority in means with a 0.65 cm non-inferiority margin at 6 months.

H_0 : The change (C) in subject's VAS pain intensity score relative to baseline at the Primary Efficacy Assessment in the Test group is worse than that of subjects in the Control group by more than 0.65 cm.

$$C_{\text{Test}} \geq C_{\text{Control}} + 0.65 \text{ cm}$$

H_1 : The change (C) in subject's VAS pain intensity score relative to baseline at the Primary Efficacy Assessment in the Test group is no more than 0.65 cm worse than the mean change from baseline in the control group.

$$C_{\text{Test}} < C_{\text{Control}} + 0.65 \text{ cm}$$

The non-inferiority margin of 0.65 cm was selected based on a previous study of a similar therapy against traditional SCSⁱ. In that study, the experimental therapy showed a 4.9 point improvement while traditional SCS showed a 3.6 point improvement for a difference of 1.3 points. Taking 50% of this treatment effect yields the margin of 0.65 cm. If the null hypothesis is successfully rejected for the non-inferiority test, a test for superiority of treatment to control will be performed based on a two-sided 0.05 alpha level.

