The following secondary endpoints do not have an associated hypothesis, and no significance level will be assigned to statistical tests that may be performed.

- Comparison of Back Pain Treatment Success (responder rate), measured as subjects with at least a 50% reduction in Back Pain VAS, between test and control
- Comparison of mean change from Baseline in Back Pain VAS, between test and control.

Repeated measures models will be used to produce estimates for these two secondary endpoints, with graphical presentation of the responder rates and mean changes from baseline.

Analysis of results through 6 months will be based on the mITT population. For time points after 6 months where crossover is allowed, crossover subjects will be counted as failures (i.e. non-responders) for endpoints defined in terms of responders, carrying forward the baseline (pre-treatment). Sensitivity

Statistical Analysis Plan		Page 12 of 14
Sponsor SGX International	Study EU RCT DTM SCS vs. CMM	Version 3.0

analysis of both secondary endpoints will also be performed to where crossover subjects are censored at the point of crossover.

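### The 6-month mean VAS superiority test is not conditional on the primary, so a superiority claim at two-sided 0.05 stays open after the primary fails

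*SAP*

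**What the plan says.** The primary, 6-month back-pain responders, is "evaluated with a Pearson Chi-square binomial test for superiority at the two-sided 0.05 alpha level" (SAP 5.7.1.1).

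SAP 5.7.2 then has two secondary bullets that carry hypotheses; protocol B.9.2.2 has the same two.

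- **Responders at 1, 3, 9, 12, 18 and 24 months.** This bullet opens with a condition: "If the primary efficacy endpoint in the test group is found to be superior to that in the control group, then a secondary endpoint" compares the arms at those visits.
- **Mean VAS change at 6 months.** This bullet opens without one: "Change in mean VAS will be evaluated with two-sample t-test of non-inferiority in means with a 0.65 cm non-inferiority margin at 6 months". After its own H0, H1 and the reasoning for the margin comes the only precondition for superiority: "If the null hypothesis is successfully rejected for the non-inferiority test, a test for superiority of treatment to control will be performed based on a" (the level is 0.05, two-sided).

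Below these, SAP 5.7.2 sets apart a further group: "The following secondary endpoints do not have an associated hypothesis, and no significance level will be assigned to statistical tests that may be performed". That group holds the repeated-measures comparisons. The 6-month mean VAS test stands above it, with a margin and a significance level.

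Protocol B.8.2 (Definition of Success) ties study success to the primary test alone and sets no success criteria for secondary endpoints. SAP 5.1.3 sets two-sided 0.05 as the default for each test. Neither document states an error rate for the primary and secondary tests together.

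Protocol B.7.4 lists non-inferiority and superiority tests of mean VAS change at all seven follow-up visits, whereas B.9.2.2 and SAP 5.7.2 test 6 months only.

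**The concern.** The plan makes one set of secondary superiority tests wait for a positive primary but not the secondary closest to it. Mean VAS change at 6 months uses the same scale at the same visit; SAP 5.7.1.2 itself notes that these endpoints share their underlying data. If the responder comparison misses, the plan still allows a hypothesis-tested statement that DTM SCS plus CMM is superior to CMM in mean back pain at 6 months.

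The non-inferiority step does not guard against a false claim for the device. A difference that favours the test arm at two-sided 0.05 has a confidence interval wholly on the favourable side of zero, so it also lies within the 0.65 cm margin. At stake is the credibility of a secondary effectiveness claim in a report whose primary failed.

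**Working it through.** **1. Inputs from the plan.** SAP section 4 gives "Estimated responder rate of 60% in the test group and 30% in the control group", "Significance level, alpha, of 0.05 two-sided" and "Randomization: 1:1", with 50 per group and power above 85%. The margin is 0.65 cm and mean VAS superiority is tested at two-sided 0.05. The sidedness of the non-inferiority test is not stated; one-sided 0.025 is taken from SAP 5.1.3.

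**2. The plan's own figure.** Power = Φ{[0.30·√50 − 1.96·√(2·0.45·0.55)] / √(0.6·0.4 + 0.3·0.7)} = Φ{(2.121 − 1.379)/0.671} = Φ(1.107) = 86.6%. This agrees with the stated figure. There is no stated familywise rate to reproduce.

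**3. What the non-inferiority step blocks.** Let d be test minus control in change, so that positive d is worse for test. A significantly worse result needs d > 1.96·SE, and non-inferiority needs d + 1.96·SE < 0.65. Both hold only if 3.92·SE < 0.65, that is, SE below about 0.16 cm. With SE = SD·√(2/n), the SD would have to be below about 0.8 cm at 50 per arm or 1.0 cm at 75. At plausible SDs the adverse tail is closed, so the mean VAS superiority test rejects falsely about 2.5% of the time, all in favour of test.

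**4. Rates under no effect, bivariate normal approximation.** Z1 is the primary and Z2 the mean VAS statistic, both positive in favour of test; c = 1.96 and ρ is their correlation.

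- Primary two-sided: P(|Z1| > c or Z2 > c). If independent, 1 − 0.95 × 0.975 = 7.4%.
- Claims favouring test: P(Z1 > c or Z2 > c). If independent, 1 − 0.975² = 4.9%.

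| ρ | Primary two-sided | Favouring test |
|---|---|---|
| 0.5 | 7.0% | 4.5% |
| 0.7 | 6.7% | 4.2% |
| 0.75 | 6.6% | 4.1% |
| 0.8 | 6.4% | 3.9% |

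**5. Simulation of the tests as written.** There were 60,000 null trials per setting with 50 or 75 per arm. Assumed, because the documents give no values: baseline VAS mean 7.5 cm, SD 0.8 or 1.2, limited to 6-10; SD of change 2-3 cm; follow-up limited to 0-10; no missing data. The mean change was varied to give common responder rates of about 14%, 30% and 50%.

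| Responders, both arms | ρ | Primary alone | Primary or mean VAS | Favouring test | Primary fails, mean VAS superior |
|---|---|---|---|---|---|
| about 30% | 0.75-0.77 | 4.8-5.0% | 6.3-6.5% | 3.9-4.1% | 1.5-1.6% |
| about 14% | 0.65-0.66 | 5.0-5.5% | 6.7-7.3% | 4.2-4.5% | 1.7-1.8% |
| about 50% | 0.80-0.81 | 5.5-5.8% | 6.8-7.1% | 4.1-4.2% | 1.3-1.4% |

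In the last two rows part of the excess over 5% is the chi-square test's own size. What the missing condition adds is the final column, 1.3-1.8 percentage points.

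**6. With the condition added.** Mean VAS superiority can be claimed only after the primary rejects. Under no effect, the chance of any false 6-month claim is then the primary's own: nominally 5%, or 2.5% in favour of test.

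**The case against.** The strongest reply is that nothing stated is breached. Success rests on the primary alone, SAP 5.1.3 sets a level per test, and no familywise rate is promised. That stands, and it limits the point to secondary claims. It does not explain why the responder secondaries wait for the primary while the closest secondary does not.

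A second reply is that the non-inferiority step does restrict the sequence. It does so in one direction only: it closes the adverse tail, as step 3 shows, and removes nothing in favour of test.

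A third is that SAP 5.7.2 lists a mean VAS comparison among the endpoints without a hypothesis. That entry is the repeated-measures comparison. The 6-month test has its own H0, H1, margin and level.

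A fourth is that a non-inferiority test is most informative when superiority has not been shown, so making it wait for a superior primary leaves it little to do. This is fair and is counted as a cost of the fix.

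A reader might also count a non-inferiority statement after a failed primary as a false positive. With zero effect non-inferiority is true, so it does not belong in the error rate.

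**Conclusion.** The gap is in the text of both documents: superiority on 6-month mean VAS can be tested and claimed at two-sided 0.05 after the primary fails. With no effect, the chance of any false 6-month superiority result is about 6-7% with the primary counted two-sided, or about 4-4.5% against 2.5% for claims favouring test. A failed primary followed by a false mean VAS superiority claim occurs in about 1.3-1.8% of trials. These figures depend on the assumed SDs, null responder rates and complete data, and on reading non-inferiority at one-sided 0.025.

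A reader might treat the two tests as unrestricted two-sided tests and infer 8-9% (1 − 0.95² = 9.75% if independent; 7.7-9.0% in the same simulations). The documents do not support that, because the superiority step runs only after non-inferiority is met. Nor do they support reading this as a fault in the success rule or a breach of a stated 5%. It is a modest, cheaply closed gap in the control of secondary claims.

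**What to change.** In SAP 5.7.2 and protocol B.9.2.2, give the mean VAS bullet the condition that the responder bullet already has. For example: if the primary endpoint shows superiority, 6-month mean VAS change is tested for non-inferiority and then superiority; otherwise the mean difference and its 95% CI are reported descriptively, with no claim of either.

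Reconcile protocol B.7.4 with these sections. Either limit the formal mean VAS tests to 6 months or put every listed visit under the same condition.

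The cost is one sentence in each document plus the B.7.4 correction. Data collection, sample size and the primary analysis do not change. The downside is that no formal mean VAS claim is possible if the primary misses, and the non-inferiority step then has little independent role. The change does not address multiplicity among the secondary tests once the primary has succeeded.

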5.7.2.1 Handling of Missing Data

Since the two secondary endpoints are based on the same underlying VAS data as that for the primary efficacy endpoint, a similar treatment of handling missing data will be applied for the trial phase outcomes. In particular, for subjects who have a successful Trial Phase and planned to receive a permanent implant, VAS data used for the secondary endpoints will correspond to the results observed at the corresponding collection times (i.e. 1 month, 3 months, 6 months, 9 months, 12 months, 18 months, and 24 months). For subjects who do not have a successful Trial Phase (based on subject's pain score), the VAS data for the secondary endpoints will utilize the results from the end of the Trial Phase.

Subjects who were not able to complete the Trial Phase (e.g., an adverse event experienced during the Trial Phase, physician withdrawal due to non-compliance, withdrawal of consent, etc.) will be removed from the mITT analysis data set as no back VAS pain score is available at the End of Trial visit.

In the event of missing secondary endpoint data the primary analysis of the secondary endpoints will be conducted using multiple imputation instead of the methods specified above. The multiple imputed datasets from the primary endpoint analysis will also be used for the analysis of the secondary endpoints as described in Section 5.7.1.2. The same methods will be used for the responder endpoint evaluation at 1, 3, 9, and 12 months. The evaluation of mean change in VAS at 6 months will estimate the mean change and difference in means between groups along with the associated standard errors which will then be combined across imputations. The imputation model will be extended as needed for the evaluation of the secondary endpoint at 9, 12, 18, and 24 months.

As an additional supporting analysis, likelihood based repeated measures models will be used to produce estimates for the secondary endpoints in the presence of missing data.

5.8 Poolability Analyses

All investigational sites will follow the requirements of a common protocol and standardized data collection procedures and forms. The primary efficacy endpoint will be presented separately for each site using descriptive statistics. Poolability of the primary endpoint across investigational sites will be evaluated using a logistic regression model with fixed effects for treatment, site, and treatment by site interaction. Sites enrolling less than 5 subjects will be combined to form one-quasi site. If the quasi-site exceeds the maximum enrollment allowed per investigational site, centers will be combined based on geographical proximity to form multiple quasi-sites until at least 5 subjects are included in each quasi-

Statistical Analysis Plan		Page 13 of 14
Sponsor SGX International	Study EU RCT DTM SCS vs. CMM	Version 3.0

site. If the p-value for the interaction effect is 0.05, additional exploratory analyses will be performed to understand any variations in outcomes by site.

Subgroup analyses will be presented based on the following parameters: age (<65 versus \geq 65 years of age), gender, and disease severity (< median versus \geq median baseline back pain).

5.9 Safety Analyses

Safety will be assessed by characterizing adverse events at all study visits with descriptive statistics.

All Adverse Events assessed/determined to be study-related study will document seriousness, severity, treatment/intervention provided, relationship to the device/procedure, and resolution.

Adverse events (AE) will be reported for the mITT set. A sensitivity analysis of AEs based on the ITT set will also be performed. AEs will be tabulated with the number of events and subjects with event for each event type and overall. Rates will be reported as the number of subjects who experience at least one event during the analysis interval out of the total number of subjects with follow-up to the beginning of the analysis interval. Serious adverse events will also be tabulated. The rate of all AEs and SAEs reported in the study will be reported.

All AEs and SAEs will also be summarized by relatedness as described above. Adverse events leading to death or study discontinuation will be provided in listing format.

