5.2 Analysis Sets

The following analysis sets are defined for analysis:

- Modified Intent to Treat (mITT): All randomized subjects to the test arms who successfully complete the Trial Phase and all successfully randomized subjects to the control arm.
- Intent-to-Treat (ITT): All successfully randomized subjects who met all the enrollment criteria.
- Per-Protocol (PP): All test subjects who received a permanent device implant and all control subjects who contributed their data to the primary and secondary endpoint without any major protocol deviations (that would render their data unevaluable).

The primary analysis of the primary and secondary endpoints will be performed on the mITT population. Supportive analyses will be performed for the Intent-to-Treat and Per-Protocol population.

For secondary endpoint analyses incorporating crossover data (i.e. data gathered in the post 6-month periods), sensitivity analyses will be performed to examine the impact of crossover.

If a supportive analysis set is the same as the mITT set, the results will be the same and will not be regenerated for that supportive analysis set.

Statistical Analysis Plan		Page 8 of 14
Sponsor SGX International	Study EU RCT DTM SCS vs. CMM	Version 3.0

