5.7.1.2 Handling of Missing Data

For subjects in the DTM™ SCS arm who do experience an unsuccessful Trial Phase, also referred to as a **Trial Failure**, results (i.e., VAS back scores) from the Trial Phase will be utilized for the primary endpoint. Specifically, the Trial Phase results of subjects who failed the Trial Phase will be attributed for each time point throughout the study, as if they remained in the study.

Subjects who did not complete the Trial Phase due to withdrawal (e.g., an adverse event experienced during the Trial Phase, physician withdrawal due to non-compliance, withdrawal of consent, etc.), will not be included in the mITT analysis data set.

In the event of missing primary endpoint data among the mITT subjects either randomized to control or DTM™ SCS subjects who did complete the Trial Phase, the primary analysis for the primary endpoint will be conducted using multiple imputation (MI) methodology rather than the methods specified in Section 5.7.1.1. The specified Pearson Chi-square test will be presented for the observed data as a supporting analysis.

For the MI analysis each missing datum is replaced by multiple values in multiple datasets. The imputed datasets are then analyzed and combined for inference. Since the primary efficacy, and secondary efficacy endpoints, are based on the same underlying data of change in VAS, and vary only in the parameterization (continuous VAS vs. dichotomized responder) or value used for the null hypothesis, the same imputed data sets will be used for the analysis of each endpoint. Imputation will be performed separately by treatment group.

Statistical Analysis Plan		Page 10 of 14
Sponsor SGX International	Study EU RCT DTM SCS vs. CMM	Version 3.0

For each imputation model, covariates will include:

- Baseline variables: age (years), gender, number of year(s) since diagnosed with chronic back pain, unilateral versus bilateral pain, back pain VAS
- Follow-up variables: end of trial phase back pain VAS, follow-up back pain VAS (after device activation) from 1 month through 24 months. The imputation models employed will correspond to the hypothesis being tested, for the primary and secondary endpoints through 6 months, the models will use data through 6 months. For secondary endpoints post 6 months, the model will be extended to the relevant time point.

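### The main adverse-event table uses mITT, which drops test subjects who did not complete the Trial Phase, including any who left because of an adverse event

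*SAP*

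**What the plan says.** SAP 5.9 sets the main population for safety: "Adverse events (AE) will be reported for the mITT set". It then adds: "A sensitivity analysis of AEs based on the ITT set will also be performed". On content it says: "AEs will be tabulated with the number of events and subjects with event for each event type and overall". SAEs are tabulated too, AEs leading to death or to leaving the study are listed, and an overall rate of reported AEs and SAEs is promised without naming a set.

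SAP 5.2 defines mITT as "All randomized subjects to the test arms who successfully complete the Trial Phase and all successfully randomized subjects to the control arm", and ITT as "All successfully randomized subjects who met all the enrollment criteria". No safety or as-treated set is defined.

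Two efficacy sections then settle who leaves mITT. SAP 5.7.1.2 excludes a group it describes as "Subjects who did not complete the Trial Phase due to withdrawal (e.g., an adverse event experienced during the Trial Phase", and goes on to other reasons such as non-compliance and withdrawn consent. SAP 5.7.2.1 repeats the exclusion and explains it: these subjects "will be removed from the mITT analysis data set as no back VAS pain score is available at the End of Trial visit".

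**The concern.** The reason for the exclusion belongs to efficacy. Without an End of Trial pain score there is nothing to carry into the responder analysis. That has no bearing on whether an adverse event happened, yet SAP 5.9 takes over the same set for safety.

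The exclusion also acts on one arm only. Controls have no Trial Phase, so all successfully randomized controls stay in.

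The period concerned is invasive. Epidural leads are placed at the start of the Trial Phase (protocol B.6.5). Protocol C.1 links lead placement to epidural hemorrhage, hematoma and paralysis, and B.6.21 foresees adverse events that force a subject out of the study. Documenting safety against CMM alone is a secondary objective (B.2). At stake is a lead safety table that leaves out the test subjects whose participation ended because of an early adverse event.

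**Working it through.** **1. Figures in the plan.** The documents state no AE rate, so there is none to reproduce. The relevant count is the number randomized: 100 / (1 − 0.33) = 149.3, rounded up to 150, or 75 per arm, as SAP 4 says. The 33% combines Trial Phase non-completion with exits before 6 months and is not split by arm or cause. The number excluded from mITT for an adverse event therefore cannot be derived.

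**2. Two subjects traced through SAP 5.9.** Both meet the entry criteria and both leave because of an adverse event soon after randomization.

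| Planned output | Test subject, leaves during Trial Phase | Control subject |
|---|---|---|
| Main AE and SAE tables (mITT) | not counted | counted |
| ITT sensitivity table | counted | counted |
| Listing of AEs leading to death or discontinuation | listed | listed |
| Overall rate of reported AEs and SAEs | set not named | set not named |

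The difference in the first row follows from the text and needs no assumption.

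**3. Effect on count and percentage (illustration).** Assumed inputs: 75 test subjects randomized; 65 in mITT, of whom 13 have an AE; 10 outside mITT. Of those 10, *a* leave the Trial Phase with an AE, *b* are trialed and leave without one, and the rest are never trialed and have no AE.

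- mITT rate = 13/65 = 20.0%
- Rate among trialed subjects = (13 + a) / (65 + a + b)
- Rate among all randomized = (13 + a) / 75

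| a | b | Subjects with an AE | Trialed | All randomized |
|---|---|---|---|---|
| 0 | 0 | 13 | 13/65 = 20.0% | 13/75 = 17.3% |
| 1 | 0 | 14 | 14/66 = 21.2% | 14/75 = 18.7% |
| 1 | 4 | 14 | 14/70 = 20.0% | 14/75 = 18.7% |
| 1 | 6 | 14 | 14/72 = 19.4% | 14/75 = 18.7% |

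The trialed rate equals the mITT rate when b = a(1 − p)/p. With p = 0.20 and a = 1 this is 0.80/0.20 = 4.

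The all-randomized rate can also lie above mITT. If only 3 of 75 are excluded, all with an AE, and 11 of the other 72 have one, mITT gives 11/72 = 15.3% and all randomized gives 14/75 = 18.7%.

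So the count in mITT is too low whenever a is at least 1, and the percentage has no fixed direction. SAP 5.9 bases its rates on follow-up intervals that it does not define, so these fixed denominators illustrate the planned statistic rather than reproduce it.

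**The case against.** The strongest reply is that SAP 5.9 already repairs this. The ITT table brings back every excluded subject who met the entry criteria, and the listing covers the subject who left because of an adverse event. SAP 5.4 also reports Trial Phase completion and early exits by reason. Safety is descriptive, and study success rests only on the effectiveness endpoint (protocol B.8.2, Definition of Success). On this view only the labels main and sensitivity are in dispute.

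Much of that stands, and it limits the weight of the point. What remains is that the lead table gives the lower count, through a rule unrelated to safety and applied to one arm. The listing gives events, not rates, and need not show a subject's other events. ITT omits randomized subjects who missed an entry criterion. That group is probably small, since eligibility is confirmed before randomization (B.6.2, B.6.4).

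Three stronger readings are tempting and are not supported:

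- **That the plan hides these events.** It does not, because other planned outputs show them.
- **That the test-arm AE rate is biased downward.** Only the count has a fixed direction. AE-free non-completers are removed too.
- **That the epidural abscess in the feasibility study (B.1) gives the size.** The protocol does not say when it began or whether that subject withdrew, so it is not a withdrawal rate.

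Nor does the rule remove every Trial Phase event. Subjects who complete the phase are not excluded for a missing End of Trial score. Whether trial failures belong to mITT is a separate contradiction: SAP 5.2 requires success, while under SAP 5.7.1.2 "the Trial Phase results of subjects who failed the Trial Phase will be attributed for each time point throughout the study". This point does not depend on how that is resolved.

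**Conclusion.** The point holds for the main AE and SAE tables. As written, they omit all events of any test subject who leaves during the Trial Phase because of an adverse event, and the test-arm count falls short by exactly those events. If no such withdrawal occurs, nothing is omitted for this reason. The size is unknown, and the percentages above rest on assumed inputs. This is a moderate flaw in the lead safety presentation. It does not affect the primary test or the sample size. It should be corrected before analysis, because the safety set should be fixed before the withdrawals are known.

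**What to change.** In SAP 5.2, define a safety set of all randomized subjects that does not depend on Trial Phase completion or an End of Trial VAS. In SAP 5.9:

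- Use this set for the main AE and SAE tables.
- Compare the arms as assigned up to the 6-month visit or crossover. Beyond that, an as-assigned table would count implant events of CMM crossovers under CMM.
- Summarize Trial Phase events, and events after crossover to DTM SCS, separately among subjects who had a trial lead procedure.
- Make the mITT AE table supportive.

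**Cost.** Wording in two sections and a few more table shells. AEs are already collected from enrollment (protocol B.8.2, Safety Measurements), so no new subjects or procedures are needed. Separating events by period assumes that onset dates are recorded. The CRF was not available to confirm this.

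**Downside.** The test-arm count may be higher. Test subjects who were never trialed dilute the all-randomized rate (14/75 = 18.7% against 13/65 = 20.0% in the illustration), which is why the trialed-subject summaries are needed. The 6-month visit is timed from activation in the test arm and from randomization in the control arm, so length of follow-up should be shown by arm.
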